1.3 SCHEDULE OF ACTIVITIES

The schedule of the activities is provided in [Table 1](#) to [Table 6](#).

Table 1 Schedule of Activities – Main Table, Part 1 (SAD in HV)

Period	Screening				Period 1					Follow Up Visit	Follow Up Visit	Follow Up Visit	Follow Up Visit	Early Termination
Day	Day -28 to Day -2	Day -1	Day 1	Day 2	Day 3	Day 4	Day 5	Day 6	Day 8	Day 15	Day 22	Day 43	Day 85 ^{e)}	NA
Time relative (h)	***	***	0	24	48	72	96	120	168	336	672	1008	2016	
Visit Window (days)										±1	±2	±7	±7	
In-clinic Period														
Ambulatory Visit	X					X	X	X	X	X	X	X	X	X
Informed Consent	X													
Eligibility	X	X												
Randomisation			X											
Demography	X													
Medical History	X													
Anthropometric Measurements	X													
Physical Examination ^{a)}	X	X							X	X	X	X	X	X
ECG-12 lead ^{b)}	X	X	5	X					X	X	X	X	X	X
Vital Signs	X	X	5	X	X	X	X	X	X	X	X	X	X	X
Substance Use ^{f)}	X	X												
Serology	X													
Blood Chemistry	X	X		X					X	X	X	X	X	X
Hematology	X	X		X					X	X	X	X	X	X
Urinalysis	X	X		X					X	X	X	X	X	X
Coagulation	X	X		X					X	X	X	X	X	X
Anti-Drug Antibody ^{c)}			X								X		X	
Pregnancy test	X	X										X	X	X
Out-clinic Period														
Blood PK Sample			12	3	X	X	X	X	X		X			X ^{g)}
Urine PK Sample			4											
Administration of Study Medication			X											
Adverse Events	X	X	X	X	X	X	X	X	X	X	X	X	X	
Previous and Concomitant Treatments	X	X	X	X	X	X	X	X	X	X	X	X	X	

Table 1 Schedule of Activities – Main Table, Part 1 (SAD in HV) (cont.)

- a) A complete physical examination is required at screening. At all other visits (or as clinically indicated), limited, symptom-directed physical examinations should be performed at the discretion of the Investigator. Height and weight will be recorded at the Screening visit only. BMI will be calculated at Screening.
- b) Twelve-lead ECGs will be obtained in triplicate (three consecutive interpretable 12-lead ECGs in less than 5 minutes) after the participant has been in a supine position for at least 10 minutes, and prior to dosing when applicable.
- c) Anti-drug antibody (ADA) samples to be taken pre-dose.

- e) If necessary, participants may be asked to return for additional follow-up visits.
- f) Includes alcohol testing.
- g) PK sample at early termination visit is optional.

Table 2 Schedule of Assessments – Detailed Table, Part 1 (SAD in HV)

Study Period	Day	Scheduled Time (h)	Vital Signs	ECG-12 lead	Blood PK Sample	Urine PK Sample ^a	ADA Sample	

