			Week 1		Week 2	Week 3	Week 4	Week 5							
Day	Day -29 to Day -2	Day -7 to -4	Day 1	Day 2	Day 8	Day 15	Day 22	Day 29	Day 30			14 days after last dose	28 days after last dose	56 days after last dose	84 days after last dose
Time Relative (h)	***	***	0	24	168	336	504	672	696	***					
Visit Window (days) ^{a)}												±3	±3	±7	±7
In-clinic Period ^{b)}															
Ambulatory Visit	X	X			X	X	X			X		X	X	X	X
Blood PK Sample [REDACTED]			7	X	2	2	2	7	X	X		X	X	X	X
Blood PK Sample [REDACTED]			7	X	X	2	X	7	X	X		X	X	X	X
Blood PK Sample [REDACTED]			7	X	X	X	X	7	X	X		X	X	X	X
Urine PK Sample			2					2							
NUC PK											X				
HBV DNA quant ^{e)}	X		X			X		X		X	X	X	X	X	X
HBV serology ^{e,i)}	X		X		X	X	X	X		X		X	X	X	X
HBV RNA quant ^{e)}			X	X	X	X		X		X		X	X	X	X
HBV core-related antigen ^{e)}			X		X	X		X		X		X	X	X	X
[REDACTED]															
HBV DNA Genotyping (Rebound)											X				
HBV genotyping			X												
[REDACTED]															
Adverse Events	X	X	X	X	X	X	X	X	X	X		X	X	X	X
Previous and Concomitant Treatments	X	X	X	X	X	X	X	X	X	X		X	X	X	X

Table 3 Schedule of Assessments – Main Table, Part 2a and Part 2b (CHB [REDACTED], 5 weeks) (cont.)

- a) All visits can be done ± 3 days, if applicable, with the exception of the safety and follow-up visits 56 and 84 days after last dose (± 7 days). The safety and follow-up visits in [Table 3](#) will only apply to Part 2a (for Part 2b, see [Table 5](#)).

At home nurse visits: vital signs, AEs and previous and concurrent treatments will be assessed; Blood for PK may be collected as specified, and other laboratory specimens may be collected as specified in the SoA table. ECG may be performed if appropriate. If site is not participating in home nurse visit, this will be an outpatient visit in clinic.

- b) Optional overnight stay in the clinic: On Day 1 as well as on Day 29 participants can either stay overnight in the clinic or can be discharged after completion of the 8 hours post-dose assessments and return the next morning for the subsequent assessments, at the Investigator's discretion.
- c) Complete physical examination is required. At all other visits (or as clinically indicated), limited, symptom-directed physical examinations should be performed at the discretion of the Investigator. Height and weight will be recorded at the Screening visit only. BMI will be calculated at Screening.

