4. STUDY DESIGN

4.1 OVERALL DESIGN

An overview of the study design is provided in Section 1.2.

The study will be conducted in two parts, of which Part 1 will be in healthy participants and Part 2 will be in CHB patients (see Section 1.2). All parts of the study are Observer-blind (see Section 6.3.2). All members of the project and study team who are not in direct contact with the participants may be unblinded. Part 1 will evaluate the safety, tolerability and PK of RO7239958 following subcutaneous (SC) administration of single ascending doses in healthy participants. Part 2 will evaluate the safety, tolerability, PK, and pharmacodynamics (PD) of multiple SC doses of RO7239958 in CHB patients established on NUC therapy, and comprises two subparts, Part 2a and Part 2b. Part 2 is a dose range finding study (DRF).

Part 1 – Single-Ascending Dose (SAD) Study in Healthy Participants

In Part 1, at least four cohorts will receive a single dose of RO7239958 or placebo. An optional cohort with participants receiving RO7239958 or placebo may be included, based on the need for further safety or PK data. Ten healthy participants, eight receiving RO7239958 and two receiving placebo, will be enrolled in each cohort using a 4:1 randomisation scheme. [REDACTED]

[REDACTED] Each cohort will implement sentinel dosing to monitor acute reactions over 24 hours post-dosing. Two participants will be dosed on Day 1, and at least one of two participants will have received RO7239958; the remaining eight participants shall be dosed the following day (i.e., after 24 hours) following satisfactory clinical safety review of the first two participants by the Investigator. For each cohort, safety will be monitored for 28 days (21 days for safety assessment plus 7 days of clinical safety observation), before escalating to the next cohort. A dose escalation meeting will take place prior to starting the next cohort. In all participants, safety will be monitored for a total of 12 weeks post-dosing.

Part 2 – Dose Range Finding (DRF) Study in CHB Patients

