4.1.4 Communication Strategy

Information will be communicated, as follows:

- The Investigator must confirm to the Sponsor that a participant has been dosed and provide a brief summary of the status of the participant in terms of safety and tolerability to RO7239958 or placebo, communicated by email or telephone.
- In Part 1, the Investigator will provide a safety assessment feedback to the Sponsor of the first two sentinel-dosed healthy participants of each cohort before proceeding to dosing the remaining participants.
- For all parts of the study and in the event of a dose-limiting adverse event (DLAE), the Investigator will contact the Sponsor immediately to discuss participant status and action taken or to be taken.
- After completion of each cohort in Part 1 (i.e., after the last participant in the cohort has reached the last day of the evaluation period, comprising 21 days of monitoring plus a further 7 days of clinical observation, for a total of 28 days), the Sponsor will organize a teleconference with the Investigators to discuss the safety and tolerability of RO7239958 or placebo, and to discuss the dose for the next cohort.

During each teleconference:

- Safety and tolerability (see [Appendix 2](#)) will be discussed along with the results of available PK data, in addition to safety laboratory results and any other available data that may assist the decision process.
- Dose escalation will only proceed if the Investigator and the Sponsor are satisfied with the safety profile of the previous cohort and agree to escalate to the next dose level.
- The decision of these meetings will be documented in writing and both the Sponsor and Investigator will approve the minutes of these meetings to confirm agreement.

For Part 2, a teleconference will be organized to discuss accumulated data from Arms 1 and 2 in Part 2a prior to the start of Arms 3 and 4; a teleconference will also be organized as above after completion of Arms 3 and 4 (*and optional Arm 5*) and before the start of subsequent arms in Part 2b if applicable.

In addition to these communications, the Sponsor and investigators will be in regular contact throughout the study by email or telephone, as per normal interactions during the conduct of a clinical study, and the Sponsor will arrange regular teleconferences and meetings to discuss study status.

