4.2 SCIENTIFIC RATIONALE FOR STUDY DESIGN

The study rationale is provided in Section [2.1](#).

In order to reduce safety risks, the effects of each dose level will be reviewed carefully before escalating to the next dose level. Dose escalation will take place after a review of safety, tolerability, and available PK data, as described in Section [4.1.2](#). Stopping rules are detailed in Section [4.1.3](#). The safety observation period has been set to 21 days for the safety laboratory assessments and to 28 days for adverse event monitoring, and this approach is supported by data from the BP39405 study (RO7062931) which has completed dosing in healthy participants (see the [RO7062931 Investigator's Brochure](#)).

The DRF part of the study, Part 2a, will evaluate the safety, tolerability, PK and PD effects of multiple doses of RO7239958 in CHB patients. Part 2b is an extension part of Part 2a to evaluate alternative regimens, additional safety, PK and PD data, if required.

[REDACTED] The approach is based on the consideration that the PK profile of RO7239958 is anticipated to show minimal variation between healthy participants and patients, and that the doses in Part 2 will never exceed the maximum safe dose defined in healthy volunteers in Part 1. Opening Part 2a with two parallel dosing levels will increase the likelihood of detecting antiviral activity and identifying a dose for regimen optimization in subsequent arms, while remaining within acceptable safety margins, based upon non-clinical data and data from Part 1.

In this study RO7239958 will be given as an add-on to NUC treatment. It is envisaged that in future studies RO7239958 will contribute to combination regimens with one or more antiviral agents or immune-enhancers, with the aim of inducing a HBV cure.

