8.3 ADVERSE EVENTS AND SERIOUS ADVERSE EVENTS

The definitions of an AE or SAE can be found in [Appendix 2](#). The non-serious adverse events of special interest and disease-related events and/or disease-related outcomes not qualifying as AEs or SAEs are discussed in Section [8.3.6](#) and [8.3.7](#).

The Investigator and any qualified designees are responsible for ensuring that all adverse events (including assessment of seriousness, severity and causality; see [Appendix 2](#)) are recorded on the Adverse Event eCRF and reported to the Sponsor in accordance with instructions provided in this section and in [Appendix 2](#).

Procedures used for recording adverse events are provided in [Appendix 3](#):

- Diagnosis versus signs and symptoms:
 - ISR
 - Other AEs
- AEs occurring secondary to other events
- Persistent or recurrent AEs
- Abnormal laboratory values
- Abnormal vital sign values
- Abnormal liver function tests
- Deaths
- Preexisting medical conditions
- Worsening of CHB
- Hospitalization or prolonged hospitalization

8.3.1 Time Period and Frequency for Collecting Adverse Event and Serious Adverse Event Information

The method of recording, evaluating, and assessing causality of AEs and SAEs and the procedures for completing and transmitting SAE reports are provided in [Appendix 2](#).

Investigators will seek information on adverse events at each participant's contact. All adverse events, whether reported by the participant or noted by study personnel, will be recorded in the participant's medical record and on the Adverse Event eCRF as follows:

After informed consent has been obtained **but prior to initiation of study treatment**, only serious adverse events caused by a protocol-mandated intervention should be reported (e.g., serious adverse events related to invasive procedures such as biopsies). Any other adverse event should not be reported.

After initiation of study treatment, all adverse events, regardless of relationship to study treatment, will be reported until 105 days after the last dose of study treatment.

Post-study adverse events and serious adverse events: The Investigator is not required to actively monitor participants for adverse events after the end of the adverse event reporting period (105 days after the last dose of study treatment).

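### Table 1 dates one Part 1 visit as both Day 22 and 672 h (Day 29); if Day 22 governs, the 28-day escalation period ends with no scheduled AE contact, and AE reporting to 105 days also outlasts the 84-day visit schedule

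*Combined protocol and SAP*

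**What the plan says.** **Escalation period, Part 1.** Section 4.1 states that for each cohort "safety will be monitored for 28 days (21 days for safety assessment plus 7 days of clinical safety observation", before the next cohort starts. Section 4.1.4 places the escalation teleconference after the last participant completes this period, "comprising 21 days of monitoring plus a further 7 days of clinical observation, for a total of 28 days". Section 4.2 assigns the two lengths: "21 days for the safety laboratory assessments and to 28 days for adverse event monitoring".

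**Part 1 visits.** Table 1 (Section 1.3) lists follow-up at Day 15 (±1), Day 22 (±2), Day 43 (±7) and Day 85 (±7), with hour labels 336, 672, 1008 and 2016. Its adverse event row is marked at scheduled visits only. Table 3, for Part 2, pairs Day 22 with 504 h and Day 29 with 672 h. Section 8.3.1 has investigators ask about AEs whenever they are in contact with a participant.

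**AE window.** Under Section 8.3.1, "all adverse events, regardless of relationship to study treatment, will be reported until 105 days after the last dose of study treatment", and the investigator's duty of active monitoring lapses only after that. Section 2.3 gives post-dose safety monitoring as 12 weeks. Section 4.1.1 gives follow-up as 84 days (at least 84 in Part 1). Section 8.10.3 counts four follow-up visits, and the fourth is at 84 (±7) days in Tables 1, 3 and 5. A Table 1 footnote attached to Day 85 adds: "If necessary, participants may be asked to return for additional follow-up visits".

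**Part 2b label.** Table 3 footnote a sets the ±3-day window for all visits "with the exception of the safety and follow-up visits 56 and 84 days after last dose". The parallel footnote to Table 5 names D134 and 182 instead, although Table 5's own columns read 56 and 84 days after last dose.

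**The concern.** AE incidence is part of the primary endpoint, and the 28-day review decides escalation in a first-in-human study. If the visit is on Day 22, the 7 days of clinical observation have no scheduled contact behind them. An AE that begins in that week may be recorded only at Day 43, which can be after the escalation meeting. One stopping criterion in Section 4.1.3 counts severe or otherwise significant related AEs of the same kind in two of eight participants. It does not depend on laboratory tests alone, so it needs the investigator to hear of the events.

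For the 105-day window, no scheduled contact follows the 84-day visit. New AEs after that visit are collected only if someone reports them, yet they belong to the period over which AEs are due.

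**Working it through.** 1. **Plan's own durations (Section 4.1.1).** Screening + treatment + follow-up, in weeks. Part 1: (28 + 84)/7 = 16. Part 2a: (28 + 28 + 84)/7 = 20. Part 2b: (28 + 84 + 84)/7 = 28. All three reproduce exactly, so they are built on 84 days of follow-up.

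2. **Hour labels in Table 1.** Hours = (Day − 1) × 24. Days 2, 3, 4, 5, 6, 8, 15, 43 and 85 give 24, 48, 72, 96, 120, 168, 336, 1008 and 2016, all as printed. Day 22 gives 21 × 24 = 504, but 672 is printed; 672/24 + 1 = Day 29. So 9 of 10 post-dose labels fit. However, 336, 672 and 1008 are equal steps of 336 h and would correspond to Days 15, 29 and 43, so 672 need not be a random slip.

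3. **If Day 22 governs.** Twenty-eight days after a Day 1 dose is Day 29 (by the same count, 84 days is Day 85, as in Table 1).
   - Visit windows: 22 ± 2 = Days 20–24; 43 ± 7 = Days 36–50. No scheduled contact on Days 25–35 (35 − 25 + 1 = 11 days).
   - Last contact before Day 29: 29 − 24 = 5, 29 − 22 = 7, 29 − 20 = 9 days earlier, which is 18%, 25% and 32% of 28 days.
   - Next contact after Day 29: 36 − 29 = 7, 43 − 29 = 14, 50 − 29 = 21 days later.

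4. **If 672 h governs.** Day 29 ± 2 = Days 27–31, so the 28-day point has a contact. The preceding visit is Day 15 ± 1 = Days 14–16, so 21 days after dosing (Day 22) has no visit and no laboratory sample.

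5. **105-day window.** The last visit falls 77 to 91 days after last dose. Remaining: 105 − 91 = 14, 105 − 84 = 21, 105 − 77 = 28 days (13%, 20%, 27% of 105). Follow-up to 105 days would give (28 + 105)/7 = 19, (28 + 28 + 105)/7 = 23 and (28 + 84 + 105)/7 = 31 weeks.

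6. **Table 5 footnote a.** 182 − 134 = 48 days apart, against 84 − 56 = 28 in the columns. The last dose day is an assumption because the regimens are redacted. With Day 78 (the last treatment visit in Table 5): 78 + 56 = 134 and 78 + 84 = 162. With Day 85 (end of treatment in Section 4.1.1): 141 and 169, so neither label fits.

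7. **Numbers affected (Section 9.2).** Escalation period: 40–50 in Part 1. 105-day window: 40 + 28 = 68 to 50 + 49 = 99.

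**The case against.** **The gap may not exist.** The 672 h label puts the visit at the 28-day point, and its equal spacing with the neighbouring hours gives it some weight. This stands: the certain defect is the mismatch between labels, and the gap is conditional on Day 22. The day labels and the 21-day laboratory period favour Day 22. Table 2 adds little, since it only repeats the day, and Table 3 concerns Part 2.

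**Text is missing.** Part 1 design text is redacted just before the sentinel-dosing and 28-day passage, and Table 1's footnotes run a, b, c, e, f, g. A contact described only there cannot be excluded. This also stands.

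**The 21/28 split is deliberate.** Section 4.2 explains it by experience in another study, and no passage promises a Day 29 visit. True, but the plan does not show how the extra week's observation is made. Participants have left the clinic after Day 3.

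**Safeguards.** Dose-limiting AEs trigger immediate contact with the sponsor (Section 4.1.4), and serious AEs and those of special interest are reported within 24 hours (Appendix 2). These work once the investigator knows of the event, and they narrow what can be missed.

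**105 days may be only a reporting window.** It is also the contraception and partner-pregnancy period, and a tail of spontaneous reports, follow-up of known AEs and optional visits is a plausible design. This makes the second mismatch the weaker one. It does not remove it, because Section 8.3.1 lifts active monitoring only after day 105.

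**A stronger inference from D182.** A reader might note that, with a Day 78 last dose, D182 is 182 − 78 = 104 days after it, and infer a planned Part 2b contact near day 105. The documents do not support this. On the same assumption D134 is exactly day 56 and day 84 would be D162, so a slip for D162 is the likelier explanation.

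**Conclusion.** Two inconsistencies hold, and one label needs editing.

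- **Table 1, Day 22 against 672 h:** certain. On Day 22, the escalation meeting can follow a period whose last 5 to 9 days had no scheduled AE enquiry. On 672 h, the 21-day laboratory point lacks a visit. One stated element is unsupported on either reading. Confidence in the gap itself is moderate, because of the label conflict and the redactions.
- **105 against 84 days:** certain as a mismatch, with 14 to 28 days lacking a scheduled contact for 68 to 99 planned participants. How far active contact was meant to continue is open.
- **Table 5 footnote a:** editorial only.

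A reader might go further and infer that nobody is in contact with participants in these intervals, that escalation would be unsafe, or that the AE comparison is biased. The documents do not support this. Unscheduled contacts are possible, and active and placebo share one schedule, so no between-group bias is built in. On the Day 22 reading the 21-day tests cover the laboratory criteria. Analyses are descriptive, with no hypothesis test (Section 9.1). The expected effect is late or incomplete capture of non-serious, non-dose-limiting AEs. The plan should be changed, but the point does not undermine the design.

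**What to change.** 1. Reconcile the day and hour labels of the Day 22 visit in Table 1, and check them against Table 2 and the 21-day laboratory period. If Day 22 stands, add a documented AE contact, for example by phone, at the end of the 28 days and before the escalation meeting. Cost: about 40 to 50 calls, one per Part 1 participant.
2. Reconcile the 105-day AE window with the 84-day schedule in one of two ways. Either add a phone AE contact at 105 days and restate participant duration as 19/23/31 weeks (68 to 99 calls at planned numbers, before over-enrolment or replacement), or summarise AE incidence through the last scheduled visit and list later reports separately (no calls).
3. Correct Table 5 footnote a so that it agrees with the 56- and 84-day columns. This is editorial.

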4.2.1 Rationale for Study Population

Part 1 will be conducted in healthy males and female subjects of non-childbearing potential, 18 to 65 years of age. The absence of confounding diseases and co-medications in healthy volunteers allows for a more consistent and comprehensive assessment of the drug disposition and the safety profile.

Part 2 will be conducted in CHB patients established on effective NUC therapy that have no current or previous history of cirrhosis and have preserved liver function, thus reducing the risk of liver-related adverse events. The PD effects of RO7239958 in humans can only be tested in patients with CHB and will comprise both standard and exploratory markers of antiviral activity. The results will provide essential information for supporting future development, including dose-selection for a Phase II study in CHB patients.

4.2.2 Rationale for Control Group

This study is designed to be adequate and controlled. Participants will be randomized to RO7239958 or placebo in each cohort of Part 1 and each arm of Part 2. The randomization scheme to active and placebo groups is considered necessary to generate an adequate within-study comparator dataset and allow a proper initial evaluation of the magnitude of any treatment effects. The study is Investigator/participant-blind to eliminate potential bias.

4.2.3 Rationale for Biomarker Assessments

In Part 2 of Study NP40520 blood samples will be taken at defined time-points (as shown in the Schedule of Activities, see Section 1.3) to monitor viral parameters in correlation with administered doses and PK parameters of RO7239958.

[figure not shown]
RO7239958 inhibits the expression of HBV RNA transcripts in HBV-infected human hepatocytes and suppresses production of viral proteins, including HBsAg and HBeAg. Thus, it is proposed that in Part 2, RO7239958 may cause a reduction of serum HBsAg in CHB patients. HBsAg loss is the recognized endpoint of effective antiviral therapy in international guidelines ([Terrault et al 2018](#); [EASL 2017](#); [APASL 2016](#)). The main virological end-point in Study NP40520 is therefore the time-course of serum HBsAg levels (see Section 8.1). CHB patients will have an HBsAg level > 250 IU/ml at screening and the kinetics of HBsAg decline during dosing will be monitored together with the kinetics of rebound post-dosing.

Additional parameters will include markers that are well established for the assessment of HBV treatment outcomes, including the time-course of anti-HBs levels, and evolution of HBeAg and anti-HBe status. [REDACTED]

Several exploratory virological end-points have recently emerged in the field that may provide an indication of improved virus control and achievement of a HBV cure. Among these, pregenomic HBV RNA that bypasses reverse transcription and is released in plasma is proposed to provide a direct measure of the transcriptional activity of cccDNA. Consistent with this view, in NUC-treated patients with suppressed HBV DNA, presence of detectable circulating HBV RNA signals an increased probability of HBV DNA rebound upon NUC cessation ([Wang J et al 2016](#)). [REDACTED]

Circulating HBcrAg levels provide one additional exploratory biomarker that will be monitored in patients pre-dosing, during dosing and post-dosing. HBcrAg is a composite circulating biomarker made of HBcAg (core antigen, which is part of HBV virions), HBeAg (which arises from the same open reading frame as HBcAg and is secreted), and p22cr (precore protein). Emerging data correlate HBcrAg measurements with treatment outcomes ([Mak et al 2018](#); [Chen et al 2017](#)). [REDACTED]

[figure not shown]
Patients in Part 2 will be established on effective NUC therapy at study entry and will have shown a circulating HBV DNA level below the assay lower limit of quantification for at least 6 months, and confirmed at screening. During Study NP40520, patients will be monitored to ensure that HBV DNA suppression is maintained. Patients who experience HBV DNA rebound during the study will be recalled for repeat testing. If the HBV DNA level is confirmed > 100 IU/ml, the patients will be assessed for evidence of NUC resistance using sequencing and potentially phenotyping, and the viral genotype will be determined by sequencing. In patients with no detectable HBV DNA, any sample with detectable HBV RNA will be used in an attempt to determine the HBV genotype by RNA sequencing.

[figure not shown]

[figure not shown]
In Part 2, blood and urine samples will be collected during the course of the study for the analysis of exploratory safety biomarkers (see Section 1.3). Renal tubular injury is a known potential class effect of LNA SSOs and a potential safety risk of RO7239958 based on data obtained preclinically. The FDA recently approved six urinary markers (clusterin, cystatin C, KIM-1, NAG, NGAL, and osteopontin) as an integrated composite measure (CM) of a kidney tubular injury response (FNIH and PSTC Collaboration Briefing Book). By measuring the fold change from baseline of these urine markers (normalized to urine creatinine), the CM panel is intended to: i) evaluate the likelihood of a renal injury response in an arm or dose group, and ii) complement the standard measures used for kidney safety monitoring such as serum creatinine, blood urea nitrogen (BUN), urinary albumin/creatinine ratio, and urinary total protein/creatinine ratio. The CM panel is not yet intended for individual patient safety monitoring. Due to the exploratory nature of the tests, the results will only be analyzed retrospectively and will not be used for decision making.

When measuring the above, the creatinine- and cystatin C-based estimated glomerular filtration rate (eGFR) will be also calculated by the CKD-epi equation as a standard measure of renal function (see Appendix 4 and Appendix 6).

Another potential safety risk of RO7239958 is hepatic injury, based on preclinical findings in NHPs and reflecting the intrinsic potential class effect of liver-targeted LNA SSOs. The standard liver injury markers (ALT and AST) have several limitations in terms of specificity (e.g., AST is not liver-specific), sensitivity (the rise in ALT and AST indicates that liver injury has already occurred), and prognostic value (the magnitude of the ALT elevation does not predict the patient's subsequent course). Study NP40520 will evaluate several emerging liver injury biomarkers (e.g., GLDH, MCSFR1, OPN, CK-18, ccK-18, and total HMGB1) that may complement ALT and AST and standard measures of liver function for the early detection of liver injury. Due to the exploratory nature of the tests, the results will only be analyzed retrospectively and will not be used for decision making.

